7.3.1. Pre-study Visit

A pre-study visit will occur and the eligibility of the subject for inclusion determined. COVID19 or influenza positive patients will sign an Informed Consent (paper or eConsent), and a list of current medications will be taken. Urine samples from child-bearing aged women will be collected and analyzed for pregnancy (or last menstrual cycle recorded). During this visit, any flu-like symptoms will be noted, temperature, Pulse/Ox and blood pressure will also be measured. During this pre-study visit, the patients are to continue with their normal therapy, if any.

7.3.2. Study Visit 1

Only COVID19 or influenza single positive subjects meeting enrollment criteria will be enrolled after review of health information collected in the pre-study visit. The correct use of the N115 sodium pyruvate nasal spray will be demonstrated to COVID-19 or influenza infected subjects, and the subjects that have been confirmed to have an infection will administer their first dose while monitored in the clinic or via telehealth. (Nasal spray can be delivered to patient at time of telehealth visit by currier). The patients will be told to spray each nostril three times, three times per day: morning, mid-day, and evening. Patients will also be instructed on filling out the Daily Data Log form or in the use of the clinical symptoms app, which will be used to record administration of the drug doses, any flu-like symptoms, and any perceived adverse events.

7.3.3 Study Visit 2 etc.

At home or on-site follow-up visits will occur every two days after Study Visit 1. During this visit, a nasal swab will be taken to determine if the patient still has an active infection. Temperature, Pulse/Ox and blood pressure will also be examined during these visits. Study monitors will review the Daily Data Log form/ Clinical app and compliance with study protocol of N115 administration will be reviewed. If needed, additional bottles of N115 nasal spray will

be delivered to the patient in the clinic or via currier.

This process of testing every two days will continue until the particular subject proves to be virus free (2 Log or greater decrease in viral RNA or less than 1000 viral RNA copies) or 14 days, whichever is first. When the patient is virus free, he/she will be excused from the study. If the subject is virus free, they will be asked to provide a second nasal swab within 24 hours to verify the negative result.

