5.2. Institutional Review Board

5.3 Study Objectives

Primary Objective

- a. The primary objective is to evaluate the effects of inhaled nasal sodium pyruvate (N115) in patients with confirmed COVID-19 or flu infections by determining changes in the duration of an active infection by PCR from nasal.
 Secondary Objective
- **a.** The second objective is to evaluate the ability of the inhaled nasal sodium pyruvate therapy in subjects with COVID-19 or flu infections to improve symptoms by the use of a patient diary and by collecting periodic vital signs, especially body temperature, blood pressure and pulse/Ox.

5.4. Study Design Overview

Individuals that are symptomatic for COVID19/influenza will initially be tested by Dynamic DNA Labs or Trinity Healthcare (Screening Visit). If positive for COVID19/influenza, patient will then be solicited for participation in the trial within 24 hours. After signing Informed Consent, women of child-bearing age will provide a urine sample to test for pregnancy. They will be randomly assigned to either the placebo or drug groups in a double blinded fashion and be given a data logbook, or clinical app for their phone, in which they will record the number of coughs and other flu-like symptoms they experience each day. Patients will be contacted by phone and/or sent reminders through a clinical phone app every two days to review symptoms and protocol compliance and patients will be tested via nasal swab every other day. This will continue every other day until the subject tests negative for COVID-19/ influenza (which is

defined as a 2-Log reduction in virus titer or less than 1000 copies of viral RNA) or 14 days, whichever comes first. Personnel collecting swabs will wear N95 mask and face shield, disposable examination gloves and disposable gown while collecting nasal swabs from patients. Samples will be collected outdoors, weather permitting, or in a well ventilated room in inclement weather.

6.0. The criteria for patient selection and for exclusion of patients, and an estimate of the number of patients to be studied.

6.1. Subject Selection

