6.1.1 Number of Patients to be Studied

Fifteen patients with confirmed COVID-19 infection will be enrolled in the trial in the drug group and fifteen with confirmed COVID-19 infection will be enrolled in the trial in the placebo group. An additional fifteen patients with confirmed influenza infection will be enrolled in the trial in the drug group and fifteen with confirmed influenza infection will be enrolled in the trial in the placebo group. Efforts will be made to include women and minorities. The study will be double blinded to subjects and study investigators.

6.2. Inclusion Criteria

- **6.2.1.** Individuals with a confirmed COVID-19/influenza viral infection, as determined by a qualified laboratory test. A nasal swab or saliva test analyzed by qPCR for COVID19 or rapid flu test from nasal swab for influenza.
- **6.2.2.** Individuals who agree to abstain from sexual intercourse, or agree to use condoms or vaginal diaphragms or other devices designed to prevent contraception, during the entire course of the study

6.3. Exclusion Criteria

- **6.3.1.** Viral infections other than COVID-19 or influenza.
- **6.3.2.** Clinically significant cardiac disease including uncontrolled congestive heart failure and unstable angina
- 6.3.3. Pregnancy
- **6.3.4.** Females of child bearing potential age not on adequate contraception or lactating
- **6.3.5.** Subjects receiving systemic corticosteroid treatment within one month of Screening Visit
- 6.3.6. Subjects Less than 18 years of age
- **6.3.7.** Hospitalization within last 6 months due to acute exacerbation of airway disease
- **6.3.8.** Subjects with a clinically significant abnormal chest x-ray within past 12 months
- **6.3.9.** Medication changes within one month of study entry
- **6.3.10.** Subjects who have participated in another investigation drug treatment study within the previous month.
- **6.3.11.** Subjects with a current history of alcohol or recreational drug abuse.
- **6.3.12.** Subjects who have taken dietary supplements containing pyruvate within 24 hours prior to the screening visit.

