7.3.5. Products Description (How Administered)

The product is an all-natural patented 20 mM sodium pyruvate in 0.9% sodium chloride nasal spray solution with 0.02% benzalkonium chloride as a preservative. The plastic bottle contains 30 mL. It is non-steroidal. Patients will forcibly expel air from their lungs and then will administer three sprays per nostril while inhaling strongly so that the drug is transported through the nose and into the lungs. The drug is to be administered three times per day (morning, mid-day, and evening). The product comes with instructions for administration (three sprays per nostril).

7.4 Concomitant Therapy

No concomitant therapy is prescribed for this study, but the subjects may continue to use their normal therapy as long as they list it as a current medication. The Principal Investigator may prescribe "rescue medication" should it be required by any of the patients. Patients may continue taking nutritional supplements. safety. Subjects may not use any of the following during the trial or for one week before enrollment in the trial: all intranasal medications or lavages, antihistamines, steroids or anti-inflammatory medications of any kind. Subjects also may not currently be taking any antiviral or antibiotic medications.

8.0. The Method For Determining The Dose(S) To Be Administered, The Planned Maximum Dosage, And The Duration Of Individual Patient Exposure To The Drug.

This is a constant dose study. The amount of delivered sodium pyruvate was determined in clinical trials to be three sprays of 20 mM sodium pyruvate in 0.9% sodium chloride solution per nostril, and this is repeated 3x per day (morning, midday, and evening). The dose was determined by evaluating the data from both animal and human studies (cited above).

9.0. A Description Of The Observations And Measurements To Be Made To Fulfill The Objectives Of The Study.

Observations for safety will include a pregnancy test for women of child-bearing age, blood oximetry, and vital signs.

Observations for efficacy will include evaluation of sore throat, congestion, erythema, the number of daily coughs, and flu-like symptoms. Perceived adverse events will be monitored.

Premature Withdrawal

The patients can withdraw from the study at any time, and for any reason. All data collected from these patients will be analyzed. Reasons for withdrawal will be recorded to ensure that it was not due to an adverse event.

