Test	Pre-study visit	Day 0 Visit 1	Day 2	Day 4	Day 6	Day 8, etc.
Clinic Visit or telehealth check		+	+	+	+	+
Informed Consent	+					
Medical History	+	+				
Physical Exam/	+					
Observe Administer Drug		+	+			
Pregnancy Test for Females	+					
Concurrent Medications Reviewed	+	+	+	+	+	+
Symptom Data Logbook (Clin. App.)		+	+	+	+	+
Adverse Events Reviewed		+	+	+	+	+
Nasal Swab for virus titer		+	+	+	+	+

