Subjects will use this diary card or a clinical phone app to record the number of their coughs per day and flu-like symptoms, any self-perceived adverse events, and any medication changes during the study.

17.0 Urinalysis: Samples may be taken and analyzed to determine if any females of child bearing age are pregnant

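### Section 7.3.1 accepts a recorded last menstrual cycle in place of the pregnancy test required elsewhere, so a woman can be dosed with the pregnancy exclusion (6.3.3) untested

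*Combined protocol and SAP*

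**What the plan says.** Pregnancy excludes a patient under 6.3.3. How that exclusion is checked is described in five places, all in the combined protocol and SAP.

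- Section 5.4, Study Design Overview: after consent, "women of child-bearing age will provide a urine sample to test for pregnancy".
- Section 9.0, on observations and measurements: "Observations for safety will include a pregnancy test for women of child-bearing age".
- The testing schedule table has a row "Pregnancy Test for Females", marked in the pre-study column and in no other.
- Section 7.3.1, Pre-study Visit: "Urine samples from child-bearing aged women will be collected and analyzed for pregnancy (or last menstrual cycle recorded", where the closing words are a bracketed alternative to the urine test.
- Section 17.0, Urinalysis: "Samples may be taken and analyzed to determine if any females of child bearing age are pregnant".

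Section 7.3.2 describes what follows. Eligible patients "will be enrolled after review of health information collected in the pre-study visit" and take the first dose under supervision, in the clinic or by telehealth. Two related criteria bear on the question. Exclusion 6.3.4 covers "Females of child bearing potential age not on adequate contraception or lactating". Inclusion 6.2.2 asks patients to agree to abstain or to use condoms, diaphragms or other "devices designed to prevent contraception, during the entire course of the study"; its wording evidently says the reverse of what is meant.

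**The concern.** A pregnancy exclusion is only as good as the check behind it. Three parts of the protocol make that check a test. The part written for the visit at which it is done lets staff write down a menstrual date instead. It does not say when the alternative may be used, which date would rule a woman out, or whether a test must follow.

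At stake is a safety exclusion the protocol sets for itself and then does not enforce. A site could comply fully with 7.3.1, breach 5.4, and enrol a pregnant woman. A monitor could not say with confidence whether an untested woman is a protocol deviation.

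**Working it through.** There is no stated figure to reproduce. The check is a comparison of the text, with some simple counting.

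**1. What each place requires**

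| Place | Requirement | Alternative to a test? |
|---|---|---|
| 5.4 | Urine pregnancy test after consent | No |
| 9.0 | Pregnancy test as a safety observation | No |
| Testing schedule | Pregnancy test, pre-study column | No |
| 7.3.1 | Urine test or recorded last menstrual cycle | Yes, unconditional |
| 17.0 | Urine samples may be taken | Permissive |

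Three places require a test, one allows a substitute and one is permissive. Section 17.0 need not be read as a separate rule, but it does not make the test mandatory again.

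**2. Whom the alternative covers.** Section 7.3.1 applies it to women of child-bearing age. It therefore cannot be read as an exemption for post-menopausal women only.

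**3. Whether anything later would catch a miss.** The schedule has 6 columns: pre-study, Day 0, Day 2, Day 4, Day 6, and Day 8 onward. The pregnancy test is marked in 1 of them. Section 7.3.2 adds no test before the first dose. Medical history is marked at both the pre-study visit and Day 0, so status could be asked about again, but it would not be tested.

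**4. Whether other criteria fill the gap.** Section 6.2.2 is an undertaking about conduct during the study. Section 6.3.4 excludes women on inadequate contraception or lactating. Both lower the chance that a woman entering the trial is pregnant. Neither establishes that she is not.

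**5. Exposure if a woman is cleared on a menstrual date alone**

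- Daily dose (7.3.2, 7.3.5): 3 sprays × 2 nostrils × 3 times a day = 18 sprays.
- Maximum over the study: 18 × 14 days = 252 sprays. This is a ceiling, because a patient leaves the study once virus free.
- Patients planned for N115 (6.1.1): 15 with COVID-19 + 15 with influenza = 30 of 60. This is the whole arm, both sexes and all adult ages.

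These figures describe exposure for an affected woman. They do not say how many women would be affected.

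**The case against.** The conflict in wording is hard to dispute. The case on the other side is about how much it matters.

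- **No section is said to prevail.** A site working from 5.4 or from the schedule would test. That is so, but a site working from 7.3.1 need not, and nothing in the protocol tells it otherwise.
- **Other safeguards exist.** Exclusion 6.3.4 applies at entry, 6.2.2 covers the study period, and history is taken again at Day 0. A missed pregnancy needs a woman who is on adequate contraception, pregnant nonetheless, and has a menstrual date that raises no concern. This makes the event less likely, but it still does not test 6.3.3.
- **The alternative may be deliberate.** The trial allows electronic consent, a telehealth first dose and courier delivery, and it limits staff exposure to infectious patients. Menstrual history could also document women of that age who cannot conceive. If that was the intention, the text does not limit the alternative to those women. A stated condition on its use would be a reasonable alternative to deleting it.
- **The consequence may be small.** Section 1.2 says the product has been shown safe in pregnant women, and no section identifies a fetal hazard. The documents do not allow that claim to be checked. The sponsor nevertheless excluded pregnancy and listed the test as a safety observation.
- **The exposure figures do not measure risk.** This is correct. They give only the dose an affected woman could receive.

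**Conclusion.** The concern holds. Section 7.3.1 as written allows a woman of child-bearing age to be enrolled and dosed on a recorded menstrual date, contrary to 5.4, 9.0 and the schedule, and no later scheduled test would detect the error. Confidence in the textual conflict is high. How often it would matter is unknown, because it depends on which section staff follow and on a sex and age mix that the documents do not give. Harm per case may be small if the statement in 1.2 is right. Sample size, error rates and the primary analysis are not affected. The sponsor should correct this as an eligibility and safety matter.

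**What to change.** In 7.3.1, delete the menstrual-history alternative and require a negative urine pregnancy test before randomisation and first dose for every woman of child-bearing potential. The menstrual date may be recorded in addition. In 17.0, change the permissive wording so that the sample will be taken. Record the test date and result with the eligibility data.

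The cost is two wording changes and an eligibility entry. The test is already planned, and patients are already seen in person for nasal swabs. The one added burden is that a urine result must be in hand before the first dose even when that dose is supervised by telehealth.

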18.2. Data Collection, Management, and Statistical Analysis

The data management staff at the research clinic and lab (Trinity Healthcare and Dynamic DNA Labs) will collect and manage the data. Monitoring and auditing of the data will be

conducted by a staff member of Cellular Sciences remotely.

The basic statistical analysis will be repeated measurements of Analysis of Variance using baseline measurements as a covariant per subject. Group comparisons of N115 to placebo will be analyzed by ANOVA followed by Chi Square, Fisher Exact, and other appropriate significance tests. Data will be compared to placebo controls and current publicly available matched data and observed values compared. Time dependence in viral titer reduction will also be compared. [name] will be responsible for the statistical analysis. Analysis will be performed blinded.

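### No diary entry is required before the first dose, so daily cough count and diary-recorded symptoms have no defined baseline for the adjustment in section 18.2

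*Combined protocol and SAP*

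**What the plan says.** Section 5.3 sets the secondary objective as symptom improvement, assessed "by the use of a patient diary and by collecting periodic vital signs, especially body temperature, blood pressure and pulse/Ox". Section 9.0 lists the daily number of coughs among the efficacy observations.

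The diary is the only source of a daily cough count that the protocol describes. Section 16.0 says "Subjects will use this diary card or a clinical phone app to record the number of their coughs per day and flu-like symptoms".

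On timing:
- Section 5.4, after consent: "They will be randomly assigned to either the placebo or drug groups in a double blinded fashion and be given a data logbook". Patients use it to "record the number of coughs and other flu-like symptoms they experience each day".
- Section 7.3.2 (Study Visit 1) has the patient take a supervised first dose. At the same visit, "Patients will also be instructed on filling out the Daily Data Log form or in the use of the clinical symptoms app".
- In the schedule table after section 9.0, the row "Symptom Data Logbook (Clin. App" is empty in the pre-study column and marked from Day 0 (Visit 1) onward.
- Section 7.3.1 (pre-study visit): "During this visit, any flu-like symptoms will be noted". Temperature, pulse/Ox and blood pressure are measured at that visit too.

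Section 18.2 plans a repeated-measures analysis of variance "using baseline measurements as a covariant per subject". It does not define baseline for any variable or say which outcomes the model covers.

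**The concern.** A baseline covariate has to be measured before treatment can affect it, and it helps most when taken on the same instrument as the outcome. For the diary outcomes, the plan asks for baseline adjustment but no section requires such a measurement.

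The site or the analyst would then have three choices: leave the diary outcomes unadjusted, adjust for the unstructured pre-study note, or take the Day 0 diary entry as baseline. The first loses precision and the second recovers only part of it. The third may adjust for something treatment has already changed. A pre-dose count also cannot be recovered reliably once dosing has begun.

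**Working it through.** The documents give no alpha, power, effect size or SD for these outcomes, so there is no planned figure to reproduce. The first step compares the sections. The rest is illustrative arithmetic on stated assumptions.

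**1. What pre-dose value exists for each part of the secondary outcome?**

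| Component | Pre-dose value described | Where |
|---|---|---|
| Temperature, pulse/Ox, blood pressure | Yes, measured at the pre-study visit | 7.3.1 |
| Flu-like symptoms | Noted, with no scale and no diary form | 7.3.1 |
| Symptoms on the diary or app | None required | 5.4, 7.3.2, schedule table |
| Daily cough count | None required | 5.4, 7.3.2, 16.0, schedule table |

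**2. Can Day 0 serve as baseline?** Section 7.3.2 puts diary instruction and first dose in one visit without fixing their order. A pre-dose entry is possible but not required. A count for the calendar day of Visit 1 mixes hours before and after the dose. If counting starts at the visit, the hours covered depend on the appointment: an 8 am visit leaves 16 of 24 hours (two thirds) and a 4 pm visit leaves 8 of 24 (one third). Both times are examples.

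**3. Precision.** Inputs: n = 15 per arm within each infection (6.1.1). Assumptions: two-sided alpha 0.05, 80% power, one post-baseline summary, normal approximation, and baseline to follow-up correlation r from 0.3 to 0.7. A baseline covariate removes a share r² of the outcome variance, so

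detectable difference = √(1 − r²) × (1.960 + 0.842) × √(2/15) SD, where √(2/15) = 0.365.

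| r | Variance removed (r²) | Detectable difference | Power for an assumed 0.8 SD effect | Equivalent n per arm, 15/(1 − r²) |
|---|---|---|---|---|
| 0 (no baseline) | 0% | 1.02 SD | 59% | 15 |
| 0.3 | 9% | 0.98 SD | 63% | 16.5 |
| 0.5 | 25% | 0.89 SD | 72% | 20 |
| 0.7 | 49% | 0.73 SD | 87% | 29.4 |

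If the two infections were pooled to 30 per arm, the detectable differences at r = 0, 0.5 and 0.7 would be 0.72, 0.63 and 0.52 SD.

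**4. Balance.** With 15 per arm, the chance difference between arms in starting severity has a standard error of √(2/15) = 0.365 SD. Without a diary baseline, that difference can be neither seen nor adjusted for on the outcome's own scale.

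**5. Attenuation if a post-dose Day 0 value is the covariate.** Let τ be the treatment effect on the follow-up value, f the share of τ already present in the Day 0 entry, and b the covariate slope. The adjusted estimate is τ − b·f·τ, so the proportion lost is b × f:
- f = 0.1: 5% (b = 0.5) or 7% (b = 0.7)
- f = 0.3: 15% (b = 0.5) or 21% (b = 0.7)

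Both f and b are assumed. If the Day 0 entry were made before the dose, f would be 0 and nothing would be lost.

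**The case against.** The case against has four parts.

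- **The pre-study visit supplies a baseline.** It does for vital signs, which are a named half of the secondary objective. A reader might infer that the secondary outcome as a whole lacks a pre-dose value; section 7.3.1 shows otherwise. For symptoms, the note gives a crude starting point that could carry some information, so the loss for symptoms may be smaller than the r = 0 row suggests. It does not supply a cough count.
- **Day 0 may be pre-dose.** A reader might infer that the first diary entry is necessarily contaminated by treatment. The documents do not say so; the order within Visit 1 is unstated. The gap is a missing requirement, and it leaves room for practice to differ between patients, some seen in clinic and some by telehealth.
- **The blank table cell proves little.** The pre-study cell for the clinic or telehealth visit is also empty, although that visit takes place, and the table has no vital-signs row. The table is therefore only supporting evidence. The point rests on 5.4, 7.3.2 and the absence of any described pre-dose entry.
- **Randomisation and blinding protect the comparison.** This stands. A missing baseline does not bias N115 against placebo. Nor is a flat contradiction with 18.2 shown, because 18.2 does not say which outcomes take the covariate.

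**Conclusion.** The point holds for the diary outcomes only. Followed as written, the plan need not yield any pre-dose daily cough count, or any pre-dose symptom record on the diary instrument, and it names no baseline for these variables.

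Under the assumptions above, having no baseline means a detectable difference of about 1.02 SD, against 0.89 SD (r = 0.5) or 0.73 SD (r = 0.7). It also removes the check of balance in starting severity and any measure of improvement from an untreated starting point. Attenuation is conditional: it arises only if an entry covering post-dose hours is used as the covariate, and its size depends on assumed values of slope and early effect.

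This is a weakness in a secondary outcome. It does not touch the PCR primary outcome or the validity of the randomised contrast. It is still worth correcting before enrolment, because the missing value cannot be reliably collected afterwards.

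**What to change.** - Require one diary entry, on the same form or app used later, before the first dose. It records coughs and symptoms over the previous 24 hours.
- Place it either at Visit 1 before dosing or at the pre-study visit, and use the same timing for every patient.
- In 18.2, name this entry as the baseline for the diary outcomes and state which outcomes take the baseline covariate.
- Treat the first full day after the first dose as the first post-baseline day, so that a partial Day 0 count is neither baseline nor outcome.
- Align 5.4, 7.3.2 and the schedule table with the chosen timing. If the pre-study visit is chosen, mark the logbook in that column and add the diary instruction to 7.3.1.

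The cost is one extra entry per patient and a few lines of text, with no added visit or procedure. The drawback is that the baseline is a 24-hour recall while later values are prospective counts. That difference in method applies equally to both arms, so the entry can still serve as a covariate. Absolute change from baseline should be read with more caution.

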COVID-19 and flu can be understood by the region of the lung that is infected. Mild disease will be confined to the conducting airways and severe disease will involve the gas exchange portion of the lung. Both flu and COVID-19 are a major health concern and can be devastating, especially for the elderly. COVID-19 is the disease caused by SARS-CoV2 the virus. Although much is known about the mortality of the clinical disease, much less is known about its pathobiology. Although details of the cellular responses to this virus are just emerging, a probable course of events can be postulated based on past studies with SARS-CoV. Based on the cells that are infected, COVID-19 can be divided into three phases that correspond to different clinical stages of the disease. Stage #1: Asymptomatic state (Initial 1–2 days of infection); Stage #2: Upper airway and conducting airway response (Next few days), and, Stage #3 Hypoxia, ground glass infiltrates, and progression to ARDS. Flu can also result in a descending, progressive disease resulting in pneumonia and ARDS in severe cases.

Purpose and Objectives of the Studies.

A COVID-19 Non-Steroidal Nasal Spray Treatment and Preventative that can get athletes, students and the general population, that test positive for Covid-19, back playing and back to work much faster than a 14-day quarantine and as a Preventative to help reduce the rate, duration and spread of the virus, is critical to the world. In testing patients with the saliva/sputum test developed by Yale University, it was discovered that some actively infected patients may be asymptomatic, but remain infected, in some cases for three weeks or longer. Thousands of data points have been collected with the saliva/sputum tests on the duration of the infection in COVID-19 patients. This data will be used as a historical baseline to demonstrate a reduction and duration of the infection in patients that use the N115 nasal spray.

This will be an on-going trial that will study the effects of a 20mM sodium pyruvate in 0.9% sodium chloride nasal spray solution on COVID-19 viral infections of patients with proven COVID-19 infections.

1. Nasal-pharyngeal swabs that are currently FDA approved for testing COVID-19 patients, will be used to determine if an individual is actively infected.

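### The either/or 'virus free' rule can release patients whose Day 0 load is above 10^5 while they still carry more than 1000 copies; for them it times a 2-log fall, not the end of active infection

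*Combined protocol and SAP*

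**What the plan says.** The primary objective (section 5.3) is to evaluate N115 by "determining changes in the duration of an active infection by PCR from nasal". Section 5.4 has patients swabbed every other day until they test negative, which is "defined as a 2-Log reduction in virus titer or less than 1000 copies of viral RNA", or for 14 days. Section 7.3.3 describes each follow-up visit as one at which "a nasal swab will be taken to determine if the patient still has an active infection", and continues "until the particular subject proves to be virus free (2 Log or greater decrease in viral RNA or less than 1000 viral RNA copies", again up to 14 days.

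On meeting the rule the patient leaves: "When the patient is virus free, he/she will be excused from the study". There is a check, "If the subject is virus free, they will be asked to provide a second nasal swab within 24 hours to verify the negative result", but no stricter limit is set for that second swab.

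No section requires both limbs together, caps the load that may remain, restricts the baseline load at entry, or states the unit of the 1000 copies. Section 18.2 plans repeated-measures analysis of variance with baseline as covariate and a comparison of the time course of titer reduction. It does not name the virus-free rule as an endpoint.

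**The concern.** The two limbs measure different things. Fewer than 1000 copies is an absolute state. A 2-log fall is relative to where the patient started. Joined by 'or', they let the easier limb decide, and for a high starting load that is always the relative one. Two patients who both carry 10,000 copies today are then classed oppositely: the one who started at 10^6 is virus free, and the one who started at 10^5 is still infected.

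What is at stake is the meaning of the result. The section on purpose and objectives wants infected people "back playing and back to work much faster than a 14-day quarantine". A shorter time to a 2-log fall could be reported as a shorter active infection in patients who still carry a substantial load. Because meeting either limb ends swabbing, time to below 1000 copies cannot be reconstructed afterwards for anyone released above that level. No later analysis plan can repair this.

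**Working it through.** The protocol states no figure on this point, so there is none to reproduce. The check is algebra, followed by illustrations on assumed inputs.

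**Inputs from the protocol.** The either/or rule (5.4, 7.3.3); swabs on Days 2, 4, …, 14 (7.3.3 and the testing schedule); 60 patients, being 15 per arm for each of two viruses (6.1.1). Log is read as log10, and the reference for the fall as the Day 0 load, B.

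**Threshold (exact).** With current load V, the rule is V ≤ B/100 or V < 1000, so it is met at the larger of B/100 and 1000. B/100 exceeds 1000 exactly when B > 10^5. A check on 10^6 random pairs (B, V) gave no mismatch. For B > 10^5 the rule coincides with the 2-log limb alone; for B ≤ 10^5 it coincides with the 1000-copy limb alone, apart from equality at the boundary.

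**Steady decline at d log/day, watched continuously, B > 10^5.** Time to the rule = 2/d. Time to below 1000 = (log10 B − 3)/d. The ratio is 2/(log10 B − 3), whatever d is.

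| B | Most copies allowed at a virus-free call | Fall needed to reach 1000 | Ratio of times |
|---|---|---|---|
| 10^5 or less | 1000 | 2 logs or less | 100% |
| 10^6 | 10,000 | 3 logs | 2/3 = 67% |
| 10^7 | 100,000 | 4 logs | 2/4 = 50% |
| 10^8 | 1,000,000 | 5 logs | 2/5 = 40% |

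**Same lines read on the planned 2-day swabs (decay assumed).**

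| Decay (log/day) | Rule met, B = 10^6 to 10^8 | First swab below 1000: 10^6 | 10^7 | 10^8 |
|---|---|---|---|---|
| 0.7 | Day 4 | Day 6 | Day 6 | Day 8 |
| 0.3 | Day 8 | Day 12 | Day 14 | not by Day 14 |

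At 0.3 log/day from 10^6 the load is exactly 1000 on Day 10. A strict 'less than' gives Day 12; a non-strict limit would give Day 10.

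**Simulation (all inputs assumed).** Mean baseline 10^5, 10^6, 10^7 or 10^8 with SD 1 log; mean decay 0.3, 0.5 or 0.7 log/day with log-scale SD 0.3; swab error SD 0.5 log; 200,000 patients per cell; event day set to 14 if not reached; no confirmation required on either side of the event-day comparison.

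- Virus-free calls at 1000 or more measured copies: 25–98% (25–33% at mean 10^5, 94–98% at 10^8).
- Patients measured above 10^5 at Day 0 who are nevertheless released below 1000 copies: 2–51%.
- Mean event day: 3.4–7.6 under the rule against 4.1–13.2 for first below 1000. The ratio is 82–84% at mean 10^5 and 47–57% at 10^8.

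Varying the spread of decay (log-scale SD 0 to 0.5) and of baseline (SD 1.0 or 1.5 logs) gave 24–98% for the first line and 46–84% for the ratio.

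**The case against.** The sponsor can fairly say four things.

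*Relative decline is a legitimate aim.* The section on purpose and objectives asks how fast viral load falls against Day Zero, and 18.2 compares titer reduction over time. This stands, and is why the 2-log fall should be kept as a separate measure. It does not make that fall the end of an infection.

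*The protocol never calls this rule the primary endpoint.* This also stands. The link is an inference: it is the only end-of-infection rule in the document, and 7.3.3 uses the objective's own phrase for what the swab decides.

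*The 1000-copy limit is no better validated.* True, and its unit is missing. But it is the protocol's own absolute limit, and it means the same for every patient.

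*The comparison of arms is unharmed.* The rule applies alike to both blinded arms, so the comparison is valid for the event as defined. Under steady decline from a common baseline, both times scale as 1/d, so the ratio between arms is the same under either rule before the Day 14 cut-off.

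Three stronger readings are tempting and unsupported.

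- That every patient above 10^5 leaves with more than 1000 copies. A fast decliner may pass both limits between swabs: from 10^5.5 at 0.75 log/day, Day 4 finds 10^(5.5 − 3.0), about 316 copies.
- That the treatment effect is shown to be spurious. One can invent curves that do this. From 10^7, let placebo fall 0.55 log/day, and N115 fall 1.05 to Day 2 and then 0.35. The rule gives Day 4 against Day 2, yet both first swab below 1000 on Day 8 (falls of 4.4 and 4.2 logs). That shows possibility only.
- That the historical comparison is distorted. The plan says "This data will be used as a historical baseline to demonstrate a reduction and duration of the infection in patients" but not how those durations were defined, so this cannot be judged.

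**Conclusion.** The point holds as a problem of meaning and of lost data, not of bias between arms. The threshold and the 10^5 crossover are exact given log10 and a Day 0 reference. Above 10^5 the label can be applied with up to B/100 copies remaining, the measure is time to a 2-log fall, and time to below 1000 is lost for those released above it.

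How much this matters rests on baseline loads and decay rates that the protocol does not give. On the assumed ranges it runs from modest to dominant: the mean event day is 47–84% of that for first below 1000. If few patients exceed 10^5 the effect is small. Confidence is high in the threshold and moderate in the impact. It should be fixed; the intact randomised comparison and the unknown baseline loads are why I rate it no higher.

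**What to change.** In 5.4 and 7.3.3, reserve 'negative' and 'virus free' for fewer than 1000 copies, with the unit stated, verified against that same limit on the already planned 24-hour swab. Continue the every-other-day swabs until that is met or Day 14. Report time to a 2-log fall separately, as virologic response.

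At minimum, rename the either/or event and report each limb separately. That mends the label but still loses time to below 1000 in patients who leave early.

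**Cost.** Wording in two sections and no new patients. On the simulation's assumptions, about 0.4–2.8 more swabs per patient, confirmation included, or roughly 26–167 over the 60 patients. More patients would be uncleared at the end: confirmed below 1000 is reached in 31–100%, against 97–100% for the current rule when it too is confirmed. The 31% (mean 10^8, 0.3 log/day) counts a first Day 14 result verified within the following 24 hours; without that allowance it is 19%.

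Swabbing for longer is a measurement change. The sponsor should reconcile the revised exit wording with the sections on how long the spray is used; no treatment rule is proposed here.
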